An important medical event that may not be immediately life-threatening or result in death or hospitalization, but based on medical judgment may jeopardize the subject and may require medical or surgical intervention to prevent any of the outcomes listed above (i.e., death of subject, life threatening, hospitalization, prolongation of hospitalization, congenital anomaly, or persistent or significant disability/incapacity). Additionally, any elective or spontaneous abortion or stillbirth is considered an important medical event. Examples of such events include allergic bronchospasm requiring intensive treatment in an emergency room or at home, blood dyscrasias or convulsions that do not result in inpatient hospitalization, or the development of drug dependency or drug abuse.

All adverse events reported from the time of study drug administration until 12 weeks after the end of the effect of study drug (24 weeks after the date of the last administration of study drug) will be collected, whether solicited or spontaneously reported by the subject. In addition, all SAEs and study procedure-related nonserious adverse events will be collected from the time the subject's parent or legal guardian signs the study-specific informed consent until study drug administration.

AbbVie will be responsible for Suspected Unexpected Serious Adverse Reactions (SUSAR) reporting for the Investigational Medicinal Product in accordance with global and local regulations.

Adverse events will be monitored throughout the study to identify any of special interest that may indicate a trend or risk to subjects.

Adverse Events of Special Interest

The following adverse events of special interest must be captured:

- Bone fracture/osteoporosis/osteopenia
- Slipped capital femoral epiphysis
- Neuropsychiatric events
- Seizure/convulsion
- Injection site reaction*
- Hypersensitivity reaction

*All injection site reactions, whether associated with study drug administration or with the stimulation test, must be captured as adverse events. Any injection site reaction that reaches seriousness criteria as stated above will be captured as an SAE and reported as described.

Adverse Event Severity and Relationship to Study Drug

The investigator will use the following definitions to rate the severity of each adverse event:

Mild: The adverse event is transient and easily tolerated by the subject.

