6.2 Other Safety Data Collection

Disease-Related Events

Abnormal laboratory, diagnostic procedural, or physical examination findings related to the disease under study will not be captured as an adverse event, unless the investigator deemed appropriate. Findings such as progression of pubertal staging are not considered to be adverse events but should be recorded in the subject's source documents and appropriate eCRF.

Drug-Related Events

LA is known to cause gonadotropins and sex steroids to temporarily rise above baseline levels because of the stimulatory effects of the drug within the first several weeks following initial administration. Therefore, an increase in clinical signs and symptoms, such as menses or spotting in females and behavioral changes in males, may occur at this time. These events should be recorded in the subject's source documents and appropriate eCRF.

The investigator will assess the subject for any LA-related symptoms at office visits or during parent or legal guardian phone calls that occur after each injection of study drug, whether expected or

unexpected; any worsening of pre-existing conditions (such as rapid progression of CPP symptoms) will be reviewed to determine whether they should be reported as adverse events.

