7.4 Statistical Analyses for Safety

Analysis of safety will be detailed in the SAP.

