3.21 Hormonal Flare and Acute-on-Chronic Response Assessment

Blood samples for AOC biochemical assessment of basal hormones (FSH, LH, and estradiol in females or testosterone in males) will be collected as follows:

Part 1: Week 1 and 48 hours after the second injection of LA 45 mg 6-month at Week 24 in all subjects enrolled.

Part 2: 48 hours after the injection of LA 45 mg 6-month at Weeks 48, 72, 96, and 120 in those subjects who are randomly selected for AOC biochemical assessment. Subjects will be randomly assigned to the AOC subgroup at Week 48 when the visit is registered in IRT.

Following each injection of LA 45 mg 6-month, the sites (or home healthcare nurse if applicable) will assess clinical signs and symptoms of hormonal flare and AOC response to an increase in sex steroids (e.g., breast tenderness and vaginal discharge in female subjects; frequent or prolonged erections, age-inappropriate behavior that may be sexual in nature in male subjects; or in both female and male subjects, exacerbation or acceleration of pubertal symptoms, substantial mood swings, or new symptoms). Sites (or home healthcare nurse if applicable) will assess for any events on the day of each study drug injection before the subject leaves the site. Sites will call the parent or legal guardian after each study drug injection at the time points specified in Section 2.

The site will record reported events in the source documentation and on the appropriate eCRF.

If unusual or unexpected clinical effects are reported during the phone call, or are spontaneously reported by the parent or legal guardian, subjects may be asked to return to the clinic at the investigator's discretion, and have a blood sample collected for AOC biochemical assessment of basal hormone levels (LH, FSH, and estradiol in females or testosterone in males). If this occurs, the visit will be documented as an Unscheduled Visit. Refer to Section 7.5 for a sample of the Hormonal Flare and Acute-on-Chronic Hormonal Response form.

When assessing these events, refer to Section 6.1 of the protocol.

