4 SAFETY MANUAL

4.1 Methods and Timing of Safety Assessment

All SAEs and study procedure-related nonserious adverse events, will be collected from the time the subject's parent or legal guardian signed the study-specific informed consent until study drug administration.

All adverse events and SAEs will be collected whether solicited or spontaneously reported by the subject and/or parent or legal guardian from the time of study drug administration through the end of the last dosing interval (24 weeks) and the 12-week Follow-up Period.

All adverse events of special interest (bone fractures/osteoporosis/osteopenia, slipped capital femoral epiphysis, neuropsychiatric events, and seizure/convulsion, injection site reaction [associated with study drug administration or stimulation test], hypersensitivity reaction) will be collected and captured. See Protocol Section 6.1, "Adverse Events of Special Interest."

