### **9.2.1.6 Adverse Events of Special Interest**

Adverse events of special interest will be summarized by SOC and PT and will be based on standardized or company MedDRA queries (SMQs or CMQs), or based on adjudication results.

The following Adverse Events of Special Interest (AESI) will be summarized:

- Bone fracture
- Slipped capital femoral epiphysis
- Neuropsychiatric events
- Seizure/convulsion
- Injection site reaction
- Hypersensitivity reactions

Detailed information about the search criteria is provided in [Appendix A](#).

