## **Appendix A. Definition of Adverse Events of Special Interest (AESI)**

Adverse Events of Special Interest (AESI) will be identified using the following search criteria:

Item of Safety Interest	Method of Surveillance
Bone fracture	Bone fractures CMQ
Slipped capital femoral epiphysis	Fractures HLGT and Epiphyseal disorders HLT (limit to under 18 years of age)
Neuropsychiatric events	Suicide/self-injury SMQ_Narrow
Seizure/convulsion	Convulsions SMQ_Broad
Injection site reaction	Injection site reaction CMQ
Hypersensitivity reactions	Hypersensitivity SMQ Narrow

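### SAP Appendix A searches the AESI labelled neuropsychiatric events only with a suicide/self-injury query, and the SAP drops osteoporosis and osteopenia from the bone AESI

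*SAP*

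**What the plan says.** Protocol 6.1 lists six AESIs that sites must capture. One is "Bone fracture/osteoporosis/osteopenia". Another is neuropsychiatric events, given without a definition or a list of terms. Operations Manual 4.1 (Appendix F of the protocol) repeats the list: "bone fractures/osteoporosis/osteopenia, slipped capital femoral epiphysis, neuropsychiatric events", followed by seizures, injection site reactions and hypersensitivity.

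SAP 9.2.1.6 opens its own list with "The following Adverse Events of Special Interest (AESI) will be summarized". There the bone item is fracture alone, while the neuropsychiatric label is unchanged. The section says that AESIs rest on standardised or company MedDRA queries (SMQs or CMQs) or on adjudication, and refers to Appendix A for the criteria. Appendix A gives a search for every item. For neuropsychiatric events it is "Suicide/self-injury SMQ_Narrow" and nothing else. For the bone item it is a company query for bone fractures. Osteoporosis and osteopenia appear nowhere in the SAP.

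According to SAP 10.2, Appendix A was added in the third version. It stands in the current Version 4.0. Neither 10.1 nor 10.2 gives a reason for either narrowing. The AESI definitions feed the tables of 9.2.1.6 and one line of the overview in 9.2.1.1, the subjects with any treatment-emergent AESI.

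**The concern.** A reader takes a row's title as a statement of what was looked for. If the row is titled neuropsychiatric events but the search is for suicide and self-injury, a low count can be misread as an absence of psychiatric and behavioural events in general. These documents foresee such effects. Operations Manual 3.21 names, among the signs of hormonal flare, "exacerbation or acceleration of pubertal symptoms, substantial mood swings, or new symptoms", and Protocol 6.2 says of the first weeks of treatment that "behavioral changes in males, may occur at this time". If an investigator reported one of these as an adverse event, a query named for suicide and self-injury would not be expected to retrieve it.

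The bone item raises a related question. The protocol names three conditions and the SAP names one, so a reader cannot tell whether the other two were dropped on purpose, are covered by the query, or were overlooked. At stake is how faithfully the AESI tables and the any-AESI line reflect the categories that the protocol set.

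**Working it through.** The plan states no figure on this point, so there is none to reproduce. The check is an item-by-item comparison, followed by a bound.

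**Step 1. Compare the lists.**

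| Protocol 6.1 and Operations Manual 4.1 | Label in SAP 9.2.1.6 | Search in SAP Appendix A | Result |
|---|---|---|---|
| Bone fracture, osteoporosis, osteopenia | Bone fracture | Company query for bone fractures | Label shortened; coverage of the dropped terms not visible |
| Slipped capital femoral epiphysis | Kept | MedDRA group-level search | Label kept |
| Neuropsychiatric events | Kept | "Suicide/self-injury SMQ_Narrow" | Label kept; search narrower by its name |
| Seizure/convulsion | Kept | Broad convulsions SMQ | Label kept |
| Injection site reaction | Kept | Company query | Label kept |
| Hypersensitivity | Kept | Narrow hypersensitivity SMQ | Label kept |

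Of six protocol categories, five keep their label and one (bone) is shortened. Of the five, one (neuropsychiatric) has a search that its own name shows to be narrower than the label.

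**Step 2. Is there another way into the row?** SAP 9.2.1.6 allows adjudication results. Neither document describes an adjudication committee, procedure or form, and Appendix A assigns a query to every item. On the written plan, the query decides.

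**Step 3. Bound the effect.** The documents give no event rates, so the counts below are symbols or assumptions.

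- Let n be the number of subjects with a treatment-emergent neuropsychiatric event but no suicide/self-injury event, leaving aside seizures, which have their own row. The neuropsychiatric row is short by n.
- Let b be the number of subjects with osteoporosis or osteopenia reported as an adverse event and not retrieved by the bone query. From the documents b may be 0.
- Let M be the number of subjects in either group, each counted once, so M ≤ n + b.
- The shortfall s in the any-AESI line satisfies 0 ≤ s ≤ M. It is 0 if every such subject also has an AESI that is counted, and M if none has.

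With 40 planned subjects, each subject missed is 1/40 = 2.5 percentage points. For assumed values of M of 1, 2 and 4, the largest shortfall is 1/40 = 2.5, 2/40 = 5.0 and 4/40 = 10.0 percentage points. The smallest is 0 in each case.

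**Step 4. Where do the events still appear?** SAP 9.2.1.2 and 9.2.1.3 tabulate all treatment-emergent events by system organ class and preferred term. SAP 9.2.1.7 tabulates hormonal flare events and counts subjects reported with abnormal behaviour after injections.

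**The case against.** The strongest reply has four parts.

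- *Delegation.* Protocol 7.4 states "Analysis of safety will be detailed in the SAP", and the lists in Protocol 6.1 and Operations Manual 4.1 are rules for collecting data, not for analysing them. The protocol does not define the neuropsychiatric category. This stands in part: the SAP may choose a narrower search. But it carries the protocol's label over that search and gives no reason, so the mismatch remains.
- *Flare behaviour is handled elsewhere.* No document classes mood swings or behavioural changes after injection as neuropsychiatric AESIs, and SAP 9.2.1.7 summarises them. This stands. They show that behavioural effects are foreseen; they do not show what the protocol's category was meant to contain.
- *The bone query is unseen.* Its terms are not in the documents and may include the missing conditions. The activity schedule has bone-age radiographs but no bone-density measurement, so such diagnoses would arise only incidentally. This stands. Only missing words are established.
- *Adjudication.* The wording in SAP 9.2.1.6 should be acknowledged, but without a described process it does not fill the gap.

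A reader might infer more: that mood or behavioural events will vanish from the safety report, or that osteoporosis and osteopenia will be undercounted. The documents support neither. Every treatment-emergent event appears in the general tables, and the content of the bone query cannot be judged from its name alone.

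**Conclusion.** The point holds as a minor defect of AESI classification. The neuropsychiatric row, followed as written, would count suicide and self-injury only. Other neuropsychiatric adverse events would be left out of it, and would enter the any-AESI line only through another AESI in the same subject. The bone item has lost two of its three named conditions without explanation; a resulting undercount is possible but not shown.

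The size cannot be estimated from the documents. The shortfall in the any-AESI line lies between zero and the number of subjects with a missed neuropsychiatric or bone AESI. No endpoint or decision rule is affected.

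The conclusion rests on two assumptions: that the suicide/self-injury query contains what its name says, since its terms are not listed, and that no adjudication process exists outside these documents.

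**What to change.** In SAP Appendix A, do one of two things for the neuropsychiatric row:

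- use a search that matches the protocol's label, list its terms, show suicide/self-injury as a sub-row and keep seizures in their own row; or
- rename the row suicide/self-injury, in 9.2.1.6 as well, and state the departure from Protocol 6.1 with the reason.

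For the bone item, restore osteoporosis and osteopenia in 9.2.1.6 and Appendix A, and confirm that the bone query contains those terms or add them. In 9.2.1.6, either describe the adjudication process or remove the reference to it.

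The cost is SAP wording and minor reprogramming on adverse events already collected and coded. A wider neuropsychiatric search gives a higher and less specific count, which the sub-row offsets. It cannot retrieve behaviour recorded only on the flare form and never reported as an adverse event; that stays in the summary of 9.2.1.7.
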